8.1.2. Sensitivity Analysis

Sensitivity analyses will be performed by using the subjects in the PPS Period 1 population, the PPS Period 2 population, and the PPS Entire Study population respectively for the data from corresponding analysis period.

8.2. Analysis of Secondary Efficacy Endpoints

8.2.1. Analysis of Continuous Endpoints

The following secondary efficacy endpoints will be summarized using descriptive statistics such as number of observations (n), mean, standard deviation, median, minimum, and maximum by study period and visit. Also, Period 2 summaries will be done by the randomized treatment.

- CFS score and change from baseline at each visit for Period 1 and Entire Study, and change from Month 12 for each visit in Period 2. Shift tables that show the change from baseline (or Month 12) in CFS score as categorical variable will also be provided.
- Conjunctival fluorescein staining score (nasal, temporal, and total scores separately) and change from baseline at each visit for Period 1 and Entire Study, and change from Month 12 for each visit in Period 2. Shift tables for nasal and temporal conjunctival staining scores will be presented as well.

- SANDE symptoms score and change from baseline at each visit for Period 1 and Entire Study, and change from Month 12 for each visit in Period 2
- Symptoms score (5-point scale) and change from baseline at each visit, for each of the five symptoms assessed for Period 1 and Entire Study, and change from Month 12 for each visit in Period 2
- TBUT and change from baseline at each visit for Period 1 and Entire Study, and change from Month 12 for each visit in Period 2
- Schirmer test and change from baseline at Month 12 visit (Period 1), change from Month 12 visit at Month 24 and Month 36 visits (Period 2), and at each visit (Entire Study)
- Use of Artificial Tears over the last week (the average number of times per day and the number of days the artificial tears were used will be summarized separately) and change from baseline at each visit for Period 1 and Entire Study, and change from Month 12 for each visit in Period 2

In addition to descriptive statistics and shift table, mixed model for repeated measures (MMRM) will be applied to estimate the response of change from Month 12 for the following endpoints;

- CFS, Conjunctival fluorescein staining score, SANDE symptoms score, Symptoms score (5-point scale), TBUT, Schirmer test and Use of Artificial Tears over the last week.

In each endpoint, separate MMRM will be applied, and the analysis will be performed using observed case of each endpoint with the FAS population Period 2. Each model will include (randomized) treatment, visit, treatment by visit interaction as fixed effects, and the corresponding Month 12 value and geographic region (Europe vs. non-Europe) as covariates. Within-subject errors will be modeled using an unstructured (UN) covariance matrix. If there are convergence issues, covariance matrix structures other than unstructured will be tried in the following order: (1) heterogeneous Toeplitz (TOEPH), (2) heterogeneous autoregressive of order 1 (ARH(1)), (3) heterogeneous compound symmetry (CSH), and (4) compound symmetry (CS). The first covariance structure that converges will be used.

Least squares mean values for each treatment arm and the differences between least squares treatment arm means and associated 95% confidence intervals with t-distribution will be reported for each visit in addition nominal p-value.

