3.3. Sample Size Determination

The sample size of this study is not planned from a formal sample size calculation since formal statistical hypothesis testing will not be performed for the primary endpoints. In this study, we plan to enroll 350 subjects. Of the 350 subjects, it is estimated that approximately 70% (245 subjects) would become markedly improved in CFS after Month 12 and enter the Period 2 (double-masked randomized period), based on Santen previous IKERVIS studies. With a 3:2 randomization allocation ratio, a sample size of 147 for IKERVIS® and 98 for Vehicle will allow us to detect a difference of 0.4 or more in CFS score with 80% power assuming the standard deviation of the difference is 1.10.

Petroutsos *et al.* (1992) showed that after 6 years of follow-up on DED subjects, a lower-bound of the estimated complication rate was 4% in severe DED subjects. In the current study, 350 subjects treated with IKERVIS® for at least one year would have 95% power to detect at least one ocular complication that occurs at 1% rate with type I error rate of 0.05.

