5.1. Adjustments for Covariates

For better understanding the long-term efficacy of IKERVIS, model based analysis (MMRM) will be conducted with corresponding baseline of each endpoint and geographic region (Europe vs. non-Europe) as covariates. The detail of each model will be described in Section 8.

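### The Period 2 MMRM gives each endpoint one Month 12 slope for all its visits; if that association fades, late-visit differences lose a little precision and can be biased by arm-dependent dropout

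*SAP*

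**What the plan says.** SAP 8.2.1 fits a separate model to each of seven secondary endpoints, from CFS to artificial tear use: "mixed model for repeated measures (MMRM) will be applied to estimate the response of change from Month 12". The mean model is given in one sentence: "Each model will include (randomized) treatment, visit, treatment by visit interaction as fixed effects, and the corresponding Month 12 value and geographic region". The only interaction named is treatment by visit. SAP 5.1 describes the same adjustment, also without an interaction: "model based analysis (MMRM) will be conducted with corresponding baseline of each endpoint and geographic region (Europe vs. non-Europe) as covariates". SAP 4.2.2 makes the Month 12 measurement the baseline for Period 2, so the two sections agree.

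The covariance is left free: "Within-subject errors will be modeled using an unstructured (UN) covariance matrix", with simpler structures as fallbacks. For the treatment differences, "associated 95% confidence intervals with t-distribution will be reported for each visit in addition nominal p-value".

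Most endpoints have eight Period 2 visits, Month 15 to Month 36. Schirmer has only Months 24 and 36 (SAP 2.2.2 and the footnotes to SAP Table 1). SAP 5.4 calls the study's objective exploratory. The SAP's revision history says that SAS sample code was added in Section 12. That code is not in the text available for review, so only the prose can be checked.

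**The concern.** Entering the Month 12 value as a main effect assumes that it predicts the score 24 months later with the same slope as the score 3 months later. The plan lets the treatment effect vary by visit and leaves the covariance unstructured, but it holds this slope fixed. For fluctuating measures such as CFS, SANDE and TBUT, a fading association would be unsurprising. A common slope would then be a compromise: too shallow at the first visits and too steep at the last.

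The late visits are the long-term part of the randomised comparison, and each is read on its own interval. Two things are at stake: some precision at Months 30 to 36, and the model's behaviour when patients leave. The analysis relies on the fitted mean and covariance to account for missing visits, because SAP 5.2 allows no imputation.

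**Working it through.** **Inputs from the documents.** SAP 3.3: "With a 3:2 randomization allocation ratio, a sample size of 147 for IKERVIS® and 98 for Vehicle", power 80% to "detect a difference of 0.4 or more in CFS score", SD 1.10. Model terms and visits are as set out above. The significance level for the power statement is not given; I assume two-sided 0.05, which matches the 95% intervals.

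**Inputs assumed.** The documents give no visit-to-visit correlations and no Period 2 dropout rate. Both are assumed and the correlations are varied.

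**1. The plan's own figure.** SE = 1.10 × √(1/147 + 1/98) = 0.1435. Then 0.4/0.1435 = 2.788, and power = Φ(2.788 − 1.960) = 79.6%. The stated 80% reproduces.

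**2. Formula for the loss (complete data).** Let B be the Month 12 value and βj = Cov(Yj, B)/Var(B) the true slope at visit j. Modelling change instead of the score shifts every slope by −1 and alters nothing below. The common slope is the generalised least squares mean g = 1′V⁻¹β / 1′V⁻¹1, where V is the residual covariance under the common slope, iterated to convergence. With residual variance σj²,

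Var(difference at j) = (1/147 + 1/98) × [σj² + (g − βj)² Var(B)].

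Visit-specific slopes remove the second term. The variance inflation is therefore 1 + (g − βj)² Var(B)/σj², and the SE inflation is its square root.

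**3. One case in full.** Take equal variances and correlation 0.75 × 0.9^k at k quarters. The slopes fall from 0.675 to 0.323, and g = 0.547.
- Month 36: (0.547 − 0.323)² / (1 − 0.323²) = 0.0502/0.8957 = 0.056, so the SE is × 1.028.
- Month 15: (0.547 − 0.675)² / (1 − 0.675²) = 0.0164/0.5444 = 0.030, so the SE is × 1.015.

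**4. Range of assumptions: SE with common slope / SE with visit-specific slopes.**

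| Correlation at k quarters | Slope, Month 15 to 36 | g | Month 15 | Month 24 | Month 36 |
|---|---|---|---|---|---|
| Constant 0.5 | 0.50 to 0.50 | 0.50 | 1.000 | 1.000 | 1.000 |
| 0.7 × 0.95^k | 0.67 to 0.46 | 0.59 | 1.005 | 1.000 | 1.010 |
| 0.75 × 0.9^k | 0.68 to 0.32 | 0.55 | 1.015 | 1.002 | 1.028 |
| 0.75 × 0.8^k | 0.60 to 0.13 | 0.39 | 1.035 | 1.004 | 1.034 |
| AR(1), 0.9^k | 0.90 to 0.43 | 0.84 | 1.009 | 1.030 | 1.099 |
| AR(1), 0.8^k | 0.80 to 0.17 | 0.63 | 1.042 | 1.028 | 1.102 |

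A second family lets the correlation with Month 12 fall linearly, under three residual correlation patterns. The Month 36 ratios are 1.007-1.010 (0.6 to 0.4), 1.015-1.023 (0.6 to 0.3), 1.026-1.041 (0.6 to 0.2), 1.045-1.084 (0.7 to 0.2) and 1.057-1.093 (0.6 to 0).

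**5. In terms of power.** Suppose, for illustration, that the planned SE is the one with visit-specific slopes. Inflation of 2.8% gives Φ(2.788/1.028 − 1.960) = 77.4%, and 10% gives Φ(2.788/1.10 − 1.960) = 71.7%.

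**6. Against no adjustment.** For the case in step 3, the Month 36 variance is 0.8957 × 1.056 = 0.946 with the common slope and 2 − 2 × 0.323 = 1.354 for unadjusted change. The SE ratio is √(0.946/1.354) = 0.84. In the linear family the ratio is 0.75-0.98 throughout. Against an unadjusted analysis of the raw score, the common slope can be slightly worse (ratio up to 1.09) when the late correlation is about 0.2 or less.

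**7. Simulation (147 vs 98, true Month 36 difference −0.40, unstructured covariance, 150 runs per scenario).**

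| Slope pattern and dropout | Common slope | Visit-specific slopes |
|---|---|---|
| 0.6 to 0.3, none | −0.378 | −0.378 |
| 0.6 to 0.1, none | −0.398 | −0.398 |
| 0.6 to 0.3, 30%, unrelated to Month 12 | −0.401 | −0.404 |
| 0.6 to 0.1, 30%, unrelated to Month 12 | −0.400 | −0.388 |
| 0.6 to 0.3, 30%, tied to Month 12 in Vehicle only | −0.461 | −0.412 |
| 0.6 to 0.1, 30%, tied to Month 12 in Vehicle only | −0.491 | −0.413 |

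In the last two rows the Monte Carlo error of the common-slope mean is about 0.174/√150 = 0.014. Shifts of 0.061 and 0.091 are therefore well beyond noise, while those of the visit-specific model (0.012 and 0.013) are not.

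**The case against.** A reader might infer that the late differences are in fact over-adjusted, at all eight visits and for no return. The documents do not support that.

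- **Over-adjustment is conditional.** It needs a fading slope, and no correlation is given for any endpoint. With constant correlation nothing is lost. Where the slope does fade, the early visits are under-adjusted, and under moderate decay Month 24 is almost untouched.
- **The adjustment has a benefit.** It beats an unadjusted analysis of change in every case tried, and a single slope saves parameters when slopes are equal.
- **Eight visits do not apply to Schirmer**, which has two.
- **With complete data there is no bias.** Randomisation protects each visit's difference. A chance imbalance carried with the wrong coefficient is the same variance loss, not a further harm.

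Three more objections have force. The extreme figures need pure AR(1) with no visit-level measurement noise, which is unlikely for a 7-point staining grade or a visual analogue scale. For CFS, only markedly improved patients are randomised, so Month 12 CFS is at most 2 and its variance is restricted. If 45-60% of that variance remains (an assumption), the SE losses of 2.8% and 3.4% fall to about 1.3-2.1%. Finally, main-effect adjustment is a valid prespecified model, and these are exploratory analyses with nominal p-values.

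All of this limits the size of the point. It does not remove the dropout risk: Protocol 7.4 lists lack of efficacy as a reason for withdrawal, so dropout that differs by arm is plausible, though whether it would depend on the Month 12 value is unknown. The Section 12 code may already contain the interaction; that cannot be settled from the available text.

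**Conclusion.** The point holds in a limited, conditional form. As written, each endpoint has one Month 12 slope across its Period 2 visits. If the association fades, the Month 36 SE rises by about 1-4% under moderate decay and up to about 10% under pure AR(1).

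The more substantive exposure is bias of about 0.06 to 0.09 in a CFS difference of 0.40, if dropout depends on the Month 12 value differently by arm. That result rests on an assumed 30% dropout, an assumed strength of dependence and assumed correlations. It shows what can happen and does not forecast this trial.

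Severity is minor. No primary endpoint is affected, and no hypothesis test depends on these models.

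**What to change.** In SAP 8.2.1, add a Month 12 value-by-visit interaction to every MMRM, so that the terms are treatment, visit, treatment by visit, Month 12 value, Month 12 value by visit, and region. State that least squares means are evaluated at the overall mean Month 12 value. Repeat the term in SAP 5.1 and make the Section 12 sample code match.

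The cost is SAP wording and one line of code: seven extra parameters per eight-visit model with about 245 patients, and one for Schirmer. If the slopes are in fact equal, the precision loss is negligible (simulated Month 36 SE ratio 1.000 with a flat slope).

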8.2.2. Analysis of DEQS-15 Questionnaire

Dry Eye related Quality of life Score (DEQS) overall frequency score, overall degree score, and 1 item overall assessment of symptom will be summarized by visit. For these summary scores, the change from baseline will also be provided for the FAS Period 1, for the subjects who experienced marked improvement during Period 1, and for the FAS Period 2 Entire Study.

For subjects who are randomized in Period 2, the DEQS summary scores and change from Month 12 will be summarized at each visit by treatment group for data collected in Period 2 using the FAS Period 2 population.

To describe a long term effect of study treatment on the quality of life, the DEQS scores and change from baseline will be summarized for the entire 3 year period using the FAS Entire Study population.

8.2.3. Analysis of Time-to-Event Endpoints

There are two time-to-event secondary efficacy endpoints in this study:

- Occurrence and time-to-become markedly improved (defined as CFS score improvement of 2 or more on the modified Oxford scale at post-baseline)
- Occurrence and time-to-relapse (increase of CFS score of 2 or more on the modified Oxford scale)

For each endpoint, the occurrence rate will be tabulated using frequency (n) and percent (%). The time-to-event data will be summarized by median time to event and its 95% confidence interval or minimum, median and maximum in case total number of events will not be enough. Survival functions will be presented graphically with the Kaplan-Meier curve (Kaplan et al., 1958) of event plot (failure plot).

[figure not shown]

Figure 3 Kaplan-Meier Curve of Time-to-become Markedly Improved

Time-to-become markedly improved will be analyzed using the FAS Period 1 population data. Time-to-relapse will be analyzed by using the FAS Period 2 data. Median time-to-relapse, hazard ratio and 95% CI will be calculated from a Cox proportional hazards model with

geographic region (Europe vs. non-Europe) and treatment as factors, and CFS score at Month 12 in the study eye as a covariate.

8.2.4. Analysis of Others

To evaluate the magnitude of corneal cleanliness (complete resolution), proportion of subjects with 0 score of CFS will be summarized by treatment group at each visit for period 2 with FAS period 2. The number of subjects with 0 score of CFS, proportion (%) of subjects, difference of the proportion, the corresponding 95% confidence interval and p-value (Chi-square test) will be provided.

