#### 11. ASSESSMENT OF EFFICACY

# 11.1. Corneal and Conjunctival Fluorescein Staining

Corneal and conjunctival fluorescein staining will be assessed immediately following the TBUT. Reading will be performed between 1 and 4 minutes after fluorescein instillation for the TBUT, to ensure that the dye does not diffuse into stroma blurring the discrete margin of any staining defects. The eye will then be examined at the slit lamp (16X magnification) using a yellow barrier filter and cobalt blue illumination to enhance visibility of staining.

Staining using fluorescein (provided by the Sponsor) will be graded using the modified Oxford scale (7-point ordinal scale, score 0, 0.5, and 1 to 5 per area [cornea + nasal and temporal conjunctiva]) for cornea and conjunctiva separately, see Appendix A-IV. On this modified scale, the score 0 corresponds to no staining dots and the score 0.5 corresponds to one staining dot per area.

A CFS grade of 0 represents complete corneal clearing.

A negative change score from baseline (Period 1) or from Month 12 (Period 2) will indicate improvement.

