3.2. Randomization and Masking

Period 1 of the study is open-label, single arm treatment with IKERVIS®. No randomization is needed in Period 1 (from Baseline for the first 12 months of treatment).

At the beginning of Period 2, (ie. the Month 12 visit), subjects who achieve a marked improvement (ie. CFS score improvement from baseline of 2 grades or more [unless if the subject had a CFS

score of 5 at baseline, the improvement in CFS has to be 3 grades or more]) will be randomly assigned (by the IWRS/IVRS) in a 3:2 ratio to receive either IKERVIS® or Vehicle for two years in a double-masked fashion. The randomization will be stratified by region (Europe vs. non-Europe), and the permuted block randomization will be used within each stratum.

The randomization schedule will be generated and implemented using central randomization via Interactive Response Technology (Rave RTSM). Each randomized subject will receive numbered study medication kits as assigned by Rave RTSM.

Treatment assignments during the Double-Masked Treatment Period will be masked to Santen employees (except Drug Supply personnel), study subjects, and Investigators. The investigator should try to avoid breaking the masking codes. However, in case of emergency only, (i.e. serious adverse event [SAE] and only when this information influences the subject's management), the investigator is entitled to unmask the subject by using IWRS, in order to obtain the study medication information (i.e. IKERVIS® or vehicle) to immediately start the appropriate treatment [to be recorded in the source data and eCRF (electronic Case Report Form)]. A record will be made of the date, time and reason for breaking the code. The investigator should inform the Sponsor immediately after unmasking. The details of this unmasking procedure will be described in a separate document. Subjects unmasked for the management of a SAE will be discontinued from the study.

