4.3.4. Markedly Improved Status

Markedly improved patients are defined for the Period 1 portion of study. The markedly improved status is defined as:

- If a subject's study eye had CFS score of 3 or 4 at Baseline, the improvement in CFS score at a post-baseline visit has to be 2 or more on the modified Oxford scale.
- If a subject's study eye had a CFS score of 5 at Baseline, the improvement in CFS score at a post-baseline visit has to be 3 grades or more on the modified Oxford scale.

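### The Period 2 comparison of complete corneal clearing (CFS = 0) ignores Month-12 CFS and region, although the SAP's other modelled CFS comparisons adjust for both (minor)

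*SAP*

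**What the plan says.** SAP 8.2.4 takes the share of patients with CFS = 0 by arm at each Period 2 visit, in the Period 2 full analysis set, and states that the "difference of the proportion, the corresponding 95% confidence interval and p-value (Chi-square test) will be provided". No model, covariate or stratum is named. Protocol 11.1 explains the outcome: "A CFS grade of 0 represents complete corneal clearing".

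The SAP's modelled between-arm CFS analyses do adjust:

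- MMRM (SAP 8.2.1): "the corresponding Month 12 value and geographic region (Europe vs. non-Europe) as covariates".
- Cox model for relapse (SAP 8.2.3): "geographic region (Europe vs. non-Europe) and treatment as factors, and CFS score at Month 12 in the study eye as a covariate".
- SAP 5.1 sets the general policy for the MMRM only, which "will be conducted with corresponding baseline of each endpoint and geographic region (Europe vs. non-Europe) as covariates".

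Region is the stratification factor (SAP 3.2): "The randomization will be stratified by region (Europe vs. non-Europe"). Month-12 CFS is not a stratification factor.

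No other section gives an adjusted or stratified analysis of CFS = 0.

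**The concern.** Patients are randomised because their CFS has already fallen. For a baseline of 3 or 4, "the improvement in CFS score at a post-baseline visit has to be 2 or more on the modified Oxford scale" (SAP 4.3.4); for a baseline of 5 the fall must be at least 3. Some patients can therefore meet the outcome on the day they are randomised. The unadjusted comparison pools those who stay clear with those who newly clear, and leaves the balance between the two groups to chance.

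Month-12 CFS is already collected and probably predicts later clearing. Leaving it out can widen the interval. It also means that the clearing result could disagree with the adjusted CFS results only because one arm began Period 2 with more clear corneas. Comparing signs between arms in Period 2 is a stated secondary objective (SAP 2.1), and 8.2.4 promises an estimate, an interval and a p-value, not only a description.

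**Working it through.** **The plan's own figure.** The only between-arm CFS power statement is in SAP 3.3: 147 v 98, difference 0.4, SD 1.10, 80% power. With two-sided alpha 0.05 (assumed), the normal approximation gives 79.6%, so it reproduces. It concerns mean CFS and says nothing about CFS = 0.

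**Range of CFS at entry to Period 2.** The scale is 0, 0.5, 1, 2, 3, 4, 5 (Protocol 11.1).

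- Baseline 3, fall of at least 2: CFS 0, 0.5 or 1.
- Baseline 4, fall of at least 2: CFS 0, 0.5, 1 or 2.
- Baseline 5, fall of at least 3: CFS 0, 0.5, 1 or 2.

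**Assumptions.** The documents give neither the share *q* clear at Month 12 nor any later clearing rates. The rates below are assumptions, written as later clearing if clear / not clear at Month 12, IKERVIS v vehicle:

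- strong prognosis: 62/20% v 45/10%
- weak prognosis: 45/28% v 32/17%
- no prognosis: 32.5% v 20.5%

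**Precision.** Let *a*, *b* be the IKERVIS rates (clear, not clear) and *c*, *d* the vehicle rates.

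- Unadjusted variance = p1(1−p1)/147 + p0(1−p0)/98, with p1 = qa + (1−q)b and p0 = qc + (1−q)d.
- Stratified variance ≈ [qa(1−a) + (1−q)b(1−b)]/147 + [qc(1−c) + (1−q)d(1−d)]/98 + q(1−q)[(a−c) − (b−d)]²/245.

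Strong prognosis, q = 0.30: p1 = 0.326 and p0 = 0.205.

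- Unadjusted: 0.326×0.674/147 + 0.205×0.795/98 = 0.003158, SD 5.62 points.
- Stratified: 0.18268/147 + 0.13725/98 + 0.21×0.07²/245 = 0.002647, SD 5.15 points.
- Ratio 1.19; information lost = 1 − 1/1.19 = 16%.

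Simulation gave ratios of 1.19 to 1.20, that is 16 to 17%. The same formulas give 1.03 (3% lost) for weak prognosis, 1.00 for none, and 1.10 (9% lost) for strong prognosis with only 10% clear.

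**Power and disagreement.** These come from 20,000 simulated trials per setting, 147 v 98, with no region effect. The chi-square is compared with a Cochran-Mantel-Haenszel (CMH) test stratified by Month-12 CFS, 0 versus above 0. The last two columns of the 10% row come from a separate run of 200,000 trials.

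| Setting | Clear at Month 12 | Power, chi-square | Power, CMH | Estimates differ by 2 points or more | p<0.05 verdicts differ |
|---|---|---|---|---|---|
| Strong | 10% | 55% | 58% | 19% | 10% |
| Strong | 30% | 55% | 63% | 38% | 14% |
| Weak | 30% | 50% | 52% | 6.5% | 6% |
| None | 30% | 54% | 55% | 0.1% | 1.5% |

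The 1-point gap in the last row is simulation noise. Under the null, with 30% clear, type I error was 4.7 to 5.0% for the chi-square and 4.8 to 5.0% for CMH. A separate model with four Month-12 grades showed the same pattern: 82 v 81%, 73 v 76% and 58 v 69% as prognosis strengthened.

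**Chance imbalance.** The SD of the between-arm difference in the share clear at Month 12 is √[q(1−q)(1/147 + 1/98)], which is 3.9, 5.2 and 6.0 points for q = 10, 20 and 30%. An imbalance of 10 points or more, in either direction, occurs in about 1.0%, 5.5% and 9.3% of trials. At q = 30% and with the overall share held fixed, a 10-point imbalance puts IKERVIS 4 points above and vehicle 6 points below that share. It moves the unadjusted difference by 0.04×42 + 0.06×35 = 3.8 points under strong prognosis and 0.04×17 + 0.06×15 = 1.6 points under weak. The assumed true differences are 12.1 and 11.6 points.

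**The case against.** The strongest reply is that nothing here is an error. Under randomisation the chi-square is valid. SAP 5.1 ties covariates to the MMRM, and unadjusted summaries, relapse rates and Kaplan-Meier curves sit beside the models throughout SAP 8.2. CFS = 0 is not a listed endpoint (SAP 2.2); it was added in the SAP revision and placed among other analyses. No hypotheses are set (Protocol 13.1.2) and the work is exploratory (SAP 5.4). CFS itself already has an adjusted comparison, and an imbalance would be visible: "Shift tables that show the change from baseline (or Month 12) in CFS score as categorical variable will also be provided" (SAP 8.2.1). All of this stands, and it is why the point is minor. The shift tables would show an imbalance but would not correct the estimate or its interval.

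The second reply is that the size is assumed and the larger figures come from the favourable setting. This also stands: with 10% clear, or with weak prognosis, the gain is about 1 to 3 power points. The one related observation is in Protocol 4.1.1: previously improved patients in the extension study spent most time at CFS 1 or 2. It points away from high clearing, but those patients had stopped treatment, so it is indirect.

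Third, no dropout was modelled, while SAP 5.2 uses observed cases. Fewer patients lower the power of both tests. The variance ratio stays about the same if losses are similar across arms and Month-12 groups.

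**Conclusion.** The point holds as a minor improvement, not as an error or a contradiction. The between-arm clearing comparison leaves out the Month-12 value and the randomisation stratum, which the SAP's own CFS models use. Depending on how well Month-12 clearing predicts later clearing, the loss runs from nothing to about 16 or 17% of the information with 30% clear at Month 12, and to about 9% at most with 10% clear. When Month-12 CFS does not predict the outcome, adjustment costs practically nothing. These sizes rest on assumed clearing rates, no region effect and the planned 147 v 98. Type I error is not at issue, and neither the primary analysis nor any listed endpoint is affected.

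**What to change.** In SAP 8.2.4, before unmasking, make the main comparison at each visit one of these, and keep the chi-square as supportive:

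1. A logistic model with treatment, region and Month-12 CFS, reported as a standardised risk difference with 95% CI.
2. A CMH-weighted risk difference with CI and test, stratified by Month-12 CFS (0 versus above 0) and region, with a fixed rule to drop region if any stratum has an empty arm.

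The cost is one or two sentences and a little programming; every variable is already collected. Each option has a small price.

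- **Logistic model:** it needs no strata. With delta-method intervals its simulated type I error was 4.8 to 5.7% and coverage 94.3 to 95.2%. Its Wald test also showed about 3 points more power than the chi-square when Month-12 CFS had no prognostic value (57.6% v 54.2%). That comes from the unpooled variance and should not be counted as a gain from adjustment.
- **CMH:** type I error was 4.8 to 5.0%, but strata can be sparse. With an assumed 80/20 region split, four strata left an empty arm in 16% of simulated trials at 10% clear, 1.2% at 20% and 0.1% at 30%. Stratifying by Month-12 CFS alone did so in under 0.01%, with power within 0.5 points.
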